9.4.5 Laboratory Evaluations

At screening and select times during the study, blood samples will be collected for safety assessments. Up to 450 mL of blood will be drawn from each participant over the course of the year-long study. Participants may be asked to come back for additional blood draws if collected blood sample is lost or unevaluable for any reason.

Coagulation

PT(INR) and a PTT will be measured at screening and at visits specified in the Schedule of Events.

Hematology (Complete blood count (CBC) with automated differential):

White blood cell (WBC) count, red blood cell (RBC) count, hemoglobin, hematocrit, lymphocytes, neutrophils, monocytes and platelet count will be measured at Screening and at visits specified in the Schedule of events.

Serum chemistry

Electrolytes [Sodium (Na), Potassium (K), Chloride (Cl), Bicarbonate (HCO₃), Calcium (Ca), Phosphate (PO₄)], glucose, BUN (blood urea nitrogen) and Creatinine (Cr), AST, ALT and bilirubin will be measured at Screening and at visits specified in the Schedule of Events.

Creatine Phosphokinase (CPK)

CPK will be measured at Screening and at visits specified in the Schedule of Events.

HbA1c

HbA1c will be measured at Screening only.

Urinalysis

Urine samples will be tested by dipstick for glucose, protein, and hematuria at Screening and at visits specified in the Schedule of Events. If abnormal (presence of protein, hematuria, or glucose $\geq 1+$), a microscopic examination should be performed.

Serology

Antibodies to hepatitis B surface antigen (HBsAg), hepatitis C and human immunodeficiency virus will

be measured at screening only.

SARS-CoV-2 (and influenza if required per hospital policy)

A nasal or nasopharyngeal (NP) swab for a COVID-19 test at screening only (a combination COVID-19 +flu may be run if required per current hospital policy).

Pregnancy Testing

For women of child bearing potential (WOCBP), a serum pregnancy test will be obtained at screening and a urine pregnancy test will be performed prior to dosings. A negative result for urine β -HCG (test must have a sensitivity of at least 25 mIU/mL) must be available prior to each administration of Investigational product. If the β -HCG test is positive, indicating that the participant is pregnant prior to completing the specified dose regimen, then no further Investigational product will be administered. Every attempt should be made to follow pregnant participants for the remainder of the study and to determine the outcome of the pregnancy.

9.4.6 Visual Analog Scale

At select times after EP, participants will complete VAS questionnaires. A VAS consists of a horizontal line, 10 cm in length, anchored by word descriptors at each end (no pain = 0 cm; worst pain = 10 cm). Immediately after injection/EP, the participant will be instructed to mark on the line, the point that they feel represents the pain experienced related to the injection/EP procedure. The VAS will be administered immediately after EP and 5 and 10 minutes later after each injection, which are separated by 30 minutes. The VAS score is determined by measuring in centimeters from the left-hand end of the line to the point that the patient marks.

9.5 Injection and Electroporation (EP)

Injections of investigational product are immediately followed by electroporation. Participants in Cohorts A1 and A2 will receive two injections of dMAb AZD5396 and dMAb AZD8076 in the deltoid/quadriceps followed immediately by EP on Day 0. Cohorts B-G will receive two injections of dMAb AZD5396 and dMAb AZD8076 in the deltoid/quadriceps followed immediately by EP on both Days 0 and 3, for a total of 4 injections. Cohort G will also receive two injections of dMAb AZD5396 and dMAb AZD8076 in the deltoid/quadriceps followed immediately by EP on Days 28 and 31, for a total of 8 injections. If preferred or needed, both doses can be done in the deltoid region or the lateral quadriceps on Days 0, 3, 28, and/or 31.

Study Agent must not be given within 2 cm of a tattoo, scar, or active lesion/rash. Also, IM injection followed immediately by EP must not be performed in the muscle of an extremity which has any metal hardware (e.g., surgical rods, pins or joint replacements). The two injections on Days 0, 3, 28, and/or 31 will be given on the same side deltoid and lateral quadriceps (i.e., left side or right side of the body). If preferred or needed, both doses can be done in the deltoid region or the lateral quadriceps.

The side-port needle should be inserted fully with firm pressure until injection is completed, then wait for a few seconds and then removed. Training on this method of injection will be provided.

9.5.1 Management of Anxiety and Pain Due to Electroporation (EP) Procedures

In case of pain, participants may be treated with a non-narcotic analgesic (e.g., ibuprofen, ketorolac) after injection/EP. Participants who are allergic to or have contraindications to EMLA, ibuprofen,

ketorolac may be offered a suitable alternative. Medication taken for anxiety or pain management should be added to the concomitant medications.

Adequate time (~>30 minutes) for pain to subside from prior EP will be allowed for participants receiving 2 EPs/day.

9.5.2 Downloading of EP Data from CELLECTRA™ 2000 Device

Within 24 to 48 hours following each Study Treatment, data will be downloaded from the EP device and the data file that is created should be sent to the Sponsor ([name]) or designee (e.g., Inovio). Instructions on how to download the data and Sponsor contact information are provided separately. Training will also be provided.

9.6 Assessment of Laboratory Abnormalities

Blood will be drawn for coagulation, serum chemistry, hematology and CPK at the visits listed in the Schedule of Events. Urinalysis will also be performed at screening and at other specified visits.

Laboratory AEs will be assessed and graded in accordance with the “Toxicity Grading Scale for Healthy Adult and Adolescent Volunteers Enrolled in Preventive Vaccine Clinical Trials”, issued in September 2007.

9.7 Assessment of Clinical Trial Adverse Events

Participants will be queried regarding the occurrence of any adverse events including adverse events related to injection site reactions, concomitant medications and new onset illness or disease during their study visits. Participants will be reminded to contact study personnel and immediately report any event for the duration of the study. All adverse events will be captured from the time of the informed consent to study discharge. These events will be recorded on the participant’s CRF.

9.8 Assessment of Administration (Injection) Site Reactions

9.8.1 Patient Self-Evaluations

Participants record any post treatment reactions (local and systemic) and enter this information in the Participant Memory Aid (shown in [Appendix A: Participant Memory Aid](#)) on the evening of each dose and for 7 days post each dose. Local administration site reactions will be recorded using the supplied measuring tool. The study staff will review the memory aid; the reported events will be assessed for clinical significance and recorded on the CRFs as appropriate. Memory aids are collected and considered source documents.

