3.2 Primary Safety Endpoints

Safety will be described for all subjects:

1. Occurrence, nature (MedDRA systemic organ class [SOC] and preferred term [PT]), time to onset, number of days of occurrence, intensity, and relationship to investigational product of injection site reactions and systemic reactions occurring up to 7 days after administration of the investigational product
2. Occurrence, nature (MedDRA SOC and PT), time to onset, relationship to investigational product and outcome of SAEs throughout the study

3. Visual analogue scale (VAS) and (see comment) scores for injection site pain up to 7 days after administration of the investigational product
4. Occurrence of out-of-range from baseline biological test results up to 7 days post-last dose

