9.8.2 Staff Evaluations

Study staff should evaluate each unique memory aid entry according to “Toxicity Grading Scale for Healthy Adult and Adolescent Volunteers Enrolled in Preventive Vaccine Clinical Trials”, issued in September 2007 ([Appendix B: Toxicity Grading Scale](#)). Any memory aid entry determined to meet the criteria for a Grade 1 or higher adverse event must be documented as an adverse event. If the reminder memory aid entry does not meet the criteria of a Grade 1 or higher AE as per the toxicity grading scale, clinical judgment can be used to determine whether the entry should be recorded as an AE. For cases

where the reminder memory aid entry and final AE reporting (i.e., grading) do not agree, the reasoning must be recorded in the source documents.

The Investigational product administration procedure consists of insertion of the CELLECTRA™ 2000 5P-IM electroporation array needles (electrodes) through the skin and into the underlying muscle, and intramuscular injection of the Investigational product followed by delivery of the electroporation pulses. This procedure is broadly described as administration because it involves more than the injection of a drug. Attributing any reaction (e.g., pain, erythema, swelling) that is observed at or near the site of the Investigational product administration procedure to injection of the Investigational product or administration of the electroporation pulses will be difficult and is not necessary. Consequently, reactions arising from the Investigational product administration procedure may be reported as administration site or injection site reactions.

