10.8 Methods and Timing of Collection of Safety Data

Non-serious AEs and SAEs (and UADEs) will be collected for each participant from the time when informed consent is obtained, through the duration of their participation. During each Investigational product administration visit, participants will be directly observed by study personnel for at least 30 minutes after administration of Investigational product for immediate reactions. Throughout the study, participants will be queried at each study visit regarding the occurrence of any SAE or other AE that may have occurred since the last study visit. They will be reminded to contact study personnel and immediately report any serious event that occurs during the course of the study.

Sources of AEs include:

- The participant's response to questions about their health (a standard non-leading question such as 'How have you been feeling since your last visit?' is asked at each visit).

- Symptoms spontaneously reported by the participant.
- Evaluations and examinations where the findings are assessed by the investigator to be clinically significant changes or abnormalities.
- Other information relating to the participant's health becoming known to the investigator (e.g., hospitalization).

All AEs, regardless of severity, seriousness, or presumed relationship to study treatment, must be recorded using medical terminology in source documents and on the CRF. Whenever possible, a diagnosis should be documented, in lieu of symptoms. The source document and the CRF must contain the Investigator's opinion concerning the relationship of the AE to study treatment.

AEs should be described with the following attributes:

- Duration (start and end dates)
- Seriousness
- Severity
- Causality
- Action(s) taken
- Outcome

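### The clinical-significance screen in 9.8.1 and the diagnosis-for-symptoms rule in 10.8 do not fit the diary recording rule in 9.8.2, which feeds primary safety endpoint 1

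*Protocol*

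**What the plan says.** Section 3.2 makes the first primary safety endpoint the occurrence, MedDRA class and term, onset, duration in days, intensity and relationship of "injection site reactions and systemic reactions occurring up to 7 days after administration of the investigational product". Section 11.3.1 summarises these events by system organ class and preferred term, per cohort and overall, with exact 90% Clopper-Pearson intervals.

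Participants keep a diary (the memory aid). Three places in the protocol say how its entries become data:

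- **Section 9.8.1:** staff review the diary and "the reported events will be assessed for clinical significance and recorded on the CRFs as appropriate". No threshold is given, and section 9.8.2 is not mentioned.
- **Section 9.8.2:** "Study staff should evaluate each unique memory aid entry according to" the FDA toxicity scale. "Any memory aid entry determined to meet the criteria for a Grade 1 or higher adverse event must be documented as an adverse event". Below Grade 1, "clinical judgment can be used to determine whether the entry should be recorded as an AE". Where the diary and the final grading disagree, "the reasoning must be recorded in the source documents".
- **Section 10.8:** "All AEs, regardless of severity, seriousness, or presumed relationship to study treatment, must be recorded using medical terminology in source documents", and on the CRF as well. The same paragraph adds: "Whenever possible, a diagnosis should be documented, in lieu of symptoms".

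**The concern.** A test of clinical significance has no function if every Grade 1 or higher entry is an adverse event anyway. Staff who read 9.8.1 by itself could set aside mild reactions. Table 5 defines Grade 1 pain as pain that leaves activity unaffected, which is the kind of entry such a screen might remove.

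The second issue is the term recorded. If a participant ticks headache, muscle aches and tiredness on one day, 9.8.2 has each entry evaluated on its own, while 10.8 asks for one diagnosis where that is possible. The endpoint is counted by preferred term, so the two routes give different tables.

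What is at stake is whether the reaction rates mean the same thing from one participant and cohort to the next. The trial is open-label and cohorts are very small. A statistical analysis plan cannot repair this later, because it can only analyse what has reached the CRF.

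**Working it through.** No stated figure depends on this point, so the check is mainly a comparison of texts.

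**Step 1. Which entries have a fixed rule?** The diary items (Appendix A) are set against the grading rows in Table 5 and Appendix B.

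| Diary item | Own grading row? | Consequence under 9.8.2 |
|---|---|---|
| Injection-site pain | Yes | Grade 1 or higher must be an AE |
| Headache, nausea, tiredness, muscle aches | Yes | Grade 1 or higher must be an AE |
| Temperature | Yes, from 38.0 °C | Grade 1 or higher must be an AE |
| Redness | Yes, from 2.5 cm | Below 2.5 cm: staff judgment |
| Swelling | Yes, from 2.5 cm or by effect on activity | Below 2.5 cm with no effect on activity: staff judgment |
| Itching, bruising, joint pain | No | Only the general illness row could apply, and the protocol does not say to use it. Arguably staff judgment |

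So 9.8.2 settles the items that have a row, once they reach Grade 1. Sections 9.7 and 10.8 agree with it. Discretion remains in the last three rows of the table. Itching is not a marginal item: Table 1 lists injection-site pruritus as very common (at least 10%), and section 9.4.1 names it among the local reactions to assess.

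**Step 2. Where does the diagnosis rule apply?** For local reactions, 9.8.2 asks for the most specific injection-site term, which largely protects them. No such instruction covers systemic symptoms, and 10.8 makes no exception for those that the diary solicits.

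**Step 3. What can one reclassified participant do?** The shift in a rate is 100/N percentage points, with N taken from section 11.4:

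- N = 3: 100/3 = 33.3
- N = 5: 100/5 = 20.0
- N = 6: 100/6 = 16.7
- N = 24: 100/24 = 4.2

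**Step 4. An assumed example.** In a cohort of 6, suppose three participants tick headache. Entry by entry, headache is 3/6 = 50% (exact 90% interval 15.3% to 84.7%). If one of them has the headache absorbed into a diagnosis with another preferred term, headache becomes 2/6 = 33.3% (6.3% to 72.9%). The protocol gives no counts, so this shows the mechanism only.

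**Step 5. The outer bound.** Suppose all six report only a Grade 1 reaction.

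- All recorded: 6/6, with lower 90% limit 0.05^(1/6) = 0.607.
- None recorded: 0/6, with upper limit 1 − 0.05^(1/6) = 0.393.

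For Grade 1 entries the second result requires staff to disregard the mandatory rule in 9.8.2, so it is a limit and not an expectation.

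**The case against.** The strongest reply is that the protocol already fixes the rule. Section 9.8.1 does not say that non-significant events are left off the CRF. Its closing words can be read as pointing to the next subsection, which is specific and mandatory. Sections 9.7 and 10.8 say the same. This stands for every entry that meets a Grade 1 row. A reader might infer that three equal rules compete and leave the primary reaction rates undefined; the documents do not support that.

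A reader might also assume that Grade 1 reactions are not clinically significant by definition. The protocol contains no such definition, and section 10.1.1 defines an adverse event without a significance threshold.

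Nor is the diary the only route to the CRF. Staff assess local and systemic reactions 30 minutes after injection and at visits up to Day 10, and ask about adverse events at every visit. An entry that is not transcribed is therefore not necessarily an uncounted reaction. The diary is, however, the only daily record, which matters for the duration and intensity parts of the endpoint.

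On 10.8, the diagnosis rule is a general convention about which term to use and applies only where a diagnosis is possible. Nothing directs staff to merge solicited symptoms, and sections 9.4.1 and 9.8.2 list headache, myalgia, arthralgia and fever separately. That narrows the point but does not remove it, because no exemption is written and the endpoint is counted by term.

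**Conclusion.** The concern holds in a limited form. Section 9.8.1 states a screen that does not fit 9.8.2 or 10.8. Read together, the sections favour 9.8.2 for Grade 1 or higher entries. Real discretion is confined to entries judged below Grade 1, and that group may include three solicited symptoms without a grading row. Section 10.8 leaves open whether solicited systemic symptoms may be replaced by a diagnosis; if they are, preferred-term rates change.

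No bias of a stated size or direction is shown. A reader might infer a systematic underestimate, or take 0% against 100% as a likely discrepancy. The first has no counts behind it, and the second is only the outer bound from step 5. What can be said is that each participant classified differently moves a rate by 33, 20 or 17 points at N = 3, 5 or 6. This rests on 9.8.2 being followed as written, and on the general illness row not being routinely used for itching, bruising and joint pain. If that row is used, the discretionary set shrinks to small areas of redness and swelling.

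The point is worth correcting because these are stated rules that feed a primary safety endpoint.

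**What to change.** - **Section 9.8.1:** delete the clinical-significance clause and refer to the rule in 9.8.2. State that all solicited diary entries go onto the CRF by day and symptom, with the grade or measurement where a scale exists, whether or not the entry is also an adverse event.
- **Section 10.8:** state that, for solicited reactions within 7 days of a dose, a diagnosis may be recorded in addition but does not replace the individual symptoms.

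The cost is about two sentences and some extra data entry. The diaries are already collected as source documents, so no new information is asked of participants. Reported reaction rates may come out higher because small or ungraded reactions become visible.

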9.8.2 Staff Evaluations

Study staff should evaluate each unique memory aid entry according to “Toxicity Grading Scale for Healthy Adult and Adolescent Volunteers Enrolled in Preventive Vaccine Clinical Trials”, issued in September 2007 ([Appendix B: Toxicity Grading Scale](#)). Any memory aid entry determined to meet the criteria for a Grade 1 or higher adverse event must be documented as an adverse event. If the reminder memory aid entry does not meet the criteria of a Grade 1 or higher AE as per the toxicity grading scale, clinical judgment can be used to determine whether the entry should be recorded as an AE. For cases

where the reminder memory aid entry and final AE reporting (i.e., grading) do not agree, the reasoning must be recorded in the source documents.

The Investigational product administration procedure consists of insertion of the CELLECTRA™ 2000 5P-IM electroporation array needles (electrodes) through the skin and into the underlying muscle, and intramuscular injection of the Investigational product followed by delivery of the electroporation pulses. This procedure is broadly described as administration because it involves more than the injection of a drug. Attributing any reaction (e.g., pain, erythema, swelling) that is observed at or near the site of the Investigational product administration procedure to injection of the Investigational product or administration of the electroporation pulses will be difficult and is not necessary. Consequently, reactions arising from the Investigational product administration procedure may be reported as administration site or injection site reactions.

When evaluating administration (injection) site reactions throughout the study, it is most important to be as specific as possible by selecting the most appropriate term (see [Table 5](#) below) and use the grading scale as listed in the Toxicity Grading Scale for Healthy Adult and Adolescent Volunteers Enrolled in Preventive Vaccine Clinical Trials, issued September 2007. Administration (injection) site reactions and administration site pain will be evaluated starting immediately and at 5 and 10 minutes following injection/EP. In addition, other events associated with administration (injection) site reactions (e.g., hematoma, infection or necrosis) should also be reported with preferred terms specific for administration (injection) site reactions. Injection site systemic and local reaction assessment that consists of evaluation of the following: General: hypotension, hyperhidrosis, erythema, headache, dizziness, myalgia, arthralgia, fever, peripheral edema, and local reaction: pain, pruritis, erythema, swelling, scab, infection. Non-injection site AEs will be assessed during the entire time while at the investigator site.

Table 5. Grading Scale for Injection Site Reactions

Local Reaction to Injectable Product (Grade)	Mild (1)	Moderate (2)	Severe (3)	Potentially Life Threatening (4)
Pain	Does not interfere with activity	Repeated use of non-narcotic pain reliever >24 hours or interferes with activity	Any use of narcotic pain reliever or prevents daily activity	Emergency room visit or hospitalization
Tenderness	Mild discomfort to touch	Discomfort with movement	Significant discomfort at rest	ER visit or hospitalization
Erythema/Redness ^a	2.5-5 cm	5.1-10 cm	>10 cm	Necrosis or exfoliative dermatitis
Induration/Swelling ^b	2.5-5 cm and no interference w/ activity	5.1-10 cm or interferes with activity	>10 cm or prevents daily activity	Necrosis

September 2007 “FDA Guidance for Industry—Toxicity Grading Scale for Healthy Adult and Adolescent Volunteers Enrolled in Preventive Vaccine Clinical Trials”

- In addition to grading the measured local reaction at the greatest single diameter, the measurement should be recorded as a continuous variable
- Should be evaluated and graded using the functional scale as well as the actual measurement.

9.9 Serum Assessments

9.9.1 Pharmacokinetic Assessment

Serum samples will be collected at baseline (Day 0), on Day 3, Day 28 (cohort G), Day 31 (cohort G) prior to dosing, and at all subsequent visits (including unscheduled visits in the event that serum mAb AZD5396 and mAb AZD8076 are detected at the Day 42 (Week 6) visit). Blood will be collected for serum at each specified visit. Details on the process for serum sample collection, storage, and shipment will be provided in the Laboratory Manual. Serum samples will be evaluated to determine the expression kinetics (i.e., pharmacokinetics) of mAb AZD5396 and mAb AZD8076 upon Investigational product administration. The serum concentration–time profile of mAb AZD5396 and mAb AZD8076 (ng/mL) will be evaluated for each participant using all available time points. The maximum serum concentration (C_{max}), the minimum serum concentration (C_{min}), and the Area Under the Curve (AUC_{0-t}) in the course of the study will be calculated as the data allows. Assays to quantitatively determine mAb AZD5396 and mAb AZD8076 levels in human serum samples are currently under development and will include either a mass spectrometry assay and/or a Meso Scale Discovery (MSD) Electrochemiluminescence (ECL) assay that will be qualified for its intended purpose using the FDA Bioanalytical Method Validation Guidance for Industry as a reference.

Serum Pharmacokinetic Assay Description

A validated assays for quantification of serum concentrations of AZD5396 and mAb AZD8076 will be carried out, using the assay previously developed to assay PK of AZD1061 and AZD8895, respectively.

To measure the AZD7442 (AZD1061 and AZD8895) human serum concentration, an immunoaffinity enrichment using streptavidin magnetic beads coated with biotinylated RBD of SARS-CoV-2 followed by LC-MS/MS approach was used. Because AZD8895 and AZD1061 are too large for practical direct quantitative analysis using LC-MS/MS technology, the captured proteins are subjected to “on-bead” proteolysis with trypsin, following standard protein denaturation, reduction, and alkylation processing steps. As a result of the trypsin digestion, characteristic peptide fragments originating from AZD8895 and AZD1061 are produced. The characteristic peptides are quantified as surrogates for the AZD8895 and AZD1061 serum concentrations.

The assay method is applicable to the quantitation of AZD8895 and AZD1061 human serum concentrations within a nominal range of 0.300 to 30.0 µg/mL in 20 µL neat human serum.

